9.1 Study design

EU PAS No.: Pending

This is a non-interventional, multi-national, single-treatment arm, observational, registry-based study to investigate the long-term safety and clinical parameters of somapacitan in paediatric patients with GHD under routine clinical practice conditions. The study design is shown schematically in Figure 9-1.

Figure 9-1 Schematic diagram of the study design

Abbreviations: GHD = growth hormone deficiency, FPFV = first patient first visit, LPFV = last patient first visit, and LPLV = last patient last visit.

The study population will consist of at least 400 paediatric GHD patients from the GloBE-Reg registry treated with once-weekly somapacitan and fulfilling the eligibility criteria of the present study (see Sections 9.2.2 and 9.2.3). The total duration of the study is planned for 10 years consisting of a 5-year recruitment period in the registry followed by a follow-up period of at least 5 years. Individual patients will be followed up from inclusion into GloBE-Reg until last routine visit within the full study duration, i.e. individual follow-up time is expected to be above 5 years. Patient data are planned to be collected beyond the age of 18 years and irrespective of discontinuation of somapacitan. The main purpose of this study is to observe patients for long-term safety. The planned study duration is from Q4 2024 until Q4 2034.

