9.1.2 Treatment of patients

Patients will be treated with commercially available somapacitan according to routine clinical practice at the discretion of the treating physician. The decision to treat a patient with somapacitan will be made at the treating physician's discretion prior to, and independently from, the decision to include the patient in the GloBE-Reg registry. Novo Nordisk A/S will not provide any products for included subjects during the conduct of the study.

Data collection for the GloBE-Reg registry will happen in conjunction with the patient's usual visits in the clinic. Additionally, optional visits are allowed per local standard of care.

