9.2.2 Inclusion criteria

For an eligible patient, all inclusion criteria must be answered 'yes'.

- 1. Treated with commercially available somapacitan according to local practice at the discretion of the physician.
- 2. Primary confirmed diagnosis of GHD as per local practice.
- 3. Male or female below 18 years of age at the time of signing informed consent in the GloBE-Reg.

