9.4 Data sources

The data for this study will be drawn from GloBE-Reg. In line with EMA guidelines⁵ (EMA/426390/2021, current version), the GloBE-Reg is an international consortium-led registry project owned by the University of Glasgow, with industry partners (including Novo Nordisk A/S), major professional endocrine societies, and patient representatives, collecting real-world data on the safety and clinical parameters of several medicinal products (including somapacitan) in the field of rare bone and endocrine conditions.

The GloBE-Reg platform was initiated on 1st October 2022. ¹⁷ The registry is designed to collect information on any child or adult who is about to start a certain treatment or where treatment is being/has been considered for a bone or endocrine condition. At the time of finalising this protocol,

^aThis will be reported at shorter intervals if data allows

^bEOS will differ from patient to patient.

^cOnly for those who are expected to reach near adult height during the study.

Protocol		Date:	17 July 2024	Novo Nordisk
Study ID: NN8640-4787	CONFIDENTIAL	Version:	3.0	
UTN: U1111-1294-5941		Status:	Final	
EU PAS No.: Pending		Page:	23 of 48	

GloBE-Reg is active in several countries in Europe, US, Asia and South America. Ethics committee approvals have been obtained in these countries.

The present study will investigate the subset of the paediatric patients with GHD from GloBE-Reg treated with somapactitan. As per the protocol, the planned number of patients to be included in the study is at least 400 (both naïve and non-naïve) male or female patients (below 18 years at the time of enrolment) with confirmed diagnosis of GHD. A minimum set of parameters can be extracted from GloBE-Reg e.g., every 6 months.

Details for neoplasms, T2DM and medication errors should be recorded in GloBE-Reg and will be included in the study data for eligible patients.

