9.7.2.2 Analysis of secondary endpoints

Binary secondary endpoints:

The binary secondary endpoints include:

- Incident neoplasm
- Incident T2DM

Incidence rates will be calculated for both endpoints and compared to aggregated data of incident neoplasms from the combined NordiNET/ANSWER study⁶ and incident T2DM from the GeNeSIS study.⁹ From both studies, the incidence rates for isolated GHD will be used for comparison. The SIR with a 95% confidence interval will be used as an additional estimate for neoplasms and new-onset T2DM.

 Protocol
 Date:
 17 July 2024
 Novo Nordisk

 Study ID: NN8640-4787
 Version:
 3.0
 3.0

 UTN: U1111-1294-5941
 Status:
 Final

Page:

25 of 48

Count-data secondary endpoints:

The analyses of the following secondary endpoints (counted from the baseline (week 0) to the EOS^a) will be done in the same way as the analysis of the primary endpoint:

• Number of AEs

EU PAS No.: Pending

- Number of SAEs
- Number of serious ADRs
- Number of medication errors

Continuous secondary endpoints

For the following secondary endpoints (clinical parameters), the change will be estimated by length of follow up and treatment duration.

- Height velocity
- Change in height velocity SDS
- Change in height SDS
- Change in IGF-I SDS
- Change in bone age

Patients reaching near adult height will be evaluated at EOS only for those who are expected to reach near adult height during the study. Change in height SDS in subjects reaching near adult height will be calculated from baseline (week 0) to EOS.

Note: Near adult height can be defined as height velocity <2 cm/year over the last 9 months and chronological age >16 years (males) or >15 years (females) or bone age >16 years (males) and >15 years (females).

IGF-I SDS will be used to evaluate treatment adherence assuming an increase in IGF-I SDS represents a response to GH treatment.

To deal with patients switching medication in-study and on-treatment analyses will be performed as defined below. The analyses will be repeated separately for GH treatment naïve and non-naïve patients previously receiving other GH treatment as data allows.

In-study

The observation period represents the time frame during which patients are considered to be part of the study, regardless of their adherence to somapacitan treatment. The in-study period starts at the time of informed consent and ends at the date of whichever comes first:

- EOS visit (last visit within the study duration)

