- Withdrawal of informed consent date
- Other (e.g. patient is deceased, or physician is no longer providing data to GloBE-Reg)

On-treatment

This observation period represents the period in which patients are treated with somapacitan. This observation period is a part of the in-study observation period. The on-treatment period starts at the date of treatment start and ends at the first date of any of the following:

• Date of treatment stop of somapacitan

^aEOS will differ from patient to patient.

 Protocol
 Date:
 17 July 2024
 Novo Nordisk

 Study ID: NN8640-4787
 Version:
 3.0

 UTN: U1111-1294-5941
 Status:
 Final

 EU PAS No.: Pending
 Page:
 26 of 48

- EOS visit (last visit within the study duration)
- Withdrawal of informed consent date
- Other (e.g. patient deceased or physician no longer providing data to GloBE-Reg)

The following subgroup analyses will be performed if data allows:

- Sex
- Age groups:
 - o Females: 0-3, 4-8, 9-14, 15-18, >18 years
 - o Males: 0-3, 4-9, 10-15, 16-18, >18 years
- GH treatment dose (GH naive or non-naïve):
 - $0.04 \leq mg/kg/week \leq 0.08$
 - \circ 0.08<mg/kg/week \leq 0.16
 - o 0.16<mg/kg/week≤0.24
 - \circ 0.24<mg/kg/week \leq 0.34
- By country/regions
- By Tanner stage 1 and >=2

Age groups are different for females and males due to the different timing in puberty and in growth velocity. 19

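### The in-study period starts at registry consent rather than first somapacitan dose, so pre-exposure AEs, SAEs, neoplasms, T2DM and person-time can enter the in-study results

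*Protocol*

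**What the plan says.** Protocol 9.7.2.2 defines two observation periods.

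- **In-study:** "The in-study period starts at the time of informed consent and ends at the date of whichever comes first" of the EOS visit, withdrawal of consent or another end of data supply. It applies "regardless of their adherence to somapacitan treatment". Section 9.1 agrees: "Individual patients will be followed up from inclusion into GloBE-Reg until last routine visit within the full study duration". The consent meant is the registry consent, as inclusion criterion 3 in 9.2.2 shows: "Male or female below 18 years of age at the time of signing informed consent in the GloBE-Reg".
- **On-treatment:** "The on-treatment period starts at the date of treatment start and ends at the first date of any of the following", the list being treatment stop plus the in-study end dates. The protocol adds: "This observation period is a part of the in-study observation period".

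On the order of registration and treatment, 9.4 says the registry is meant for "any child or adult who is about to start a certain treatment or where treatment is being/has been considered" for a bone or endocrine condition, and that it opened on 1 October 2022. Section 9.1.2 says the decision to use somapacitan is made "prior to, and independently from, the decision to include the patient in the GloBE-Reg registry".

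Inclusion criterion 1 asks for somapacitan treatment without relating its start to consent. The safety analysis set (9.7.1) takes everyone exposed during the study period. Safety endpoints are counted from baseline (week 0), which is never tied to consent or to the first dose.

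**The concern.** A registry consent date is not the start of exposure. Take a child registered in 2025 on another growth hormone, or untreated, who starts somapacitan in 2027. No criterion excludes this child, and the in-study clock has already run for two years at the first dose. Events and time from those years then count in the in-study analysis of a somapacitan cohort.

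This matters because only the in-study analysis retains follow-up after somapacitan is stopped. Section 9.1 asks for that follow-up and names long-term safety as the study's main purpose. Neoplasms and T2DM are a special focus of the primary objective, yet 9.7.2.2 gives no start of risk for their incidence rates and SIRs.

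The reverse case also fails. If somapacitan began before consent, on-treatment time begins at treatment start but is declared part of a period that opens later. Both statements cannot hold for such a patient.

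**Working it through.** **Plan's own figure.** No stated number depends on this point. The only related one is the Wilson interval for a 2% ADR proportion at 400 patients, (1.02, 3.89) in Table 9-4. With p = 0.02, n = 400 and z = 1.96:

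- centre term p + z²/2n = 0.0248
- half-width z√(p(1−p)/n + z²/4n²) = 0.01454
- divisor 1 + z²/n = 1.0096

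This gives (1.02, 3.90), which agrees to within 0.01. The interval and the planned size do not change.

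**Can the first dose follow consent?** Yes. Section 9.4 admits patients before treatment. Section 9.1.2 orders two decisions, not consent and first dose. Sections 9.2.2 and 9.7.1 impose no order at all.

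**Which results are exposed?**

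| Result | Protection in the protocol | What remains |
|---|---|---|
| On-treatment analysis | Starts at treatment start (9.7.2.2) | No pre-exposure time |
| ADRs, serious ADRs | Causality judged against somapacitan (11.1); rates per exposure-year (9.7.2.1) | Little |
| In-study AEs, SAEs | Rates per exposure-year | Events before exposure can be counted without matching time |
| In-study neoplasm, T2DM | None stated | Events and time before exposure |

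**How large?** Let f be the share of patients registered before the first dose, L their mean lead in years, and T the mean in-study years. The protocol gives neither f nor L, so both are assumptions. For T, 5 and 10 years bracket the planned follow-up. The value 7.25 assumes uniform recruitment from Q4 2024 to Q4 2029 and follow-up to Q3 2034, which is 400 × 7.25 = 2,900 patient-years.

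- Pre-exposure share of in-study time: w = f × L / T.
- If the true on-drug rate ratio against the comparator is 2 and the denominator is in-study time, the observed ratio is 2(1−w) + w = 2 − w when lead-time events occur at the comparator rate. It is 2(1−w) when none are counted.
- If lead-time events are counted but the denominator is exposure time only, and rates are equal before and after the start, the rate is inflated by 1/(1−w). This assumes treatment continues to the end of follow-up.

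| f | L | T | w | True ratio 2 appears as | Inflation 1/(1−w) |
|---|---|---|---|---|---|
| 10% | 0.25 | 10 | 0.25% | 1.995 to 1.998 | 1.003 |
| 10% | 0.25 | 5 | 0.5% | 1.990 to 1.995 | 1.005 |
| 25% | 1 | 5 | 5% | 1.90 to 1.95 | 1.05 |
| 20% | 2 | 7.25 | 160/2,900 = 5.5% | 1.89 to 1.94 | 1.06 |
| 50% | 2 | 5 | 20% | 1.60 to 1.80 | 1.25 |
| 50% | 3 | 7.25 | 600/2,900 = 20.7% | 1.59 to 1.79 | 1.26 |

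If every patient registered three months early, w would be 0.25/5 = 5% at 5 years and 2.5% at 10 years. With the clock started at the later of consent and first dose, w = 0 in every row.

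**The case against.** The strongest reply is that the protocol already contains the remedies.

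- **The on-treatment analysis starts at treatment start.** This stands. A reader might infer that all somapacitan safety results are contaminated, and they are not. But the on-treatment analysis stops when treatment stops, so it cannot replace the in-study analysis for late events.
- **Rates are per patient-years of exposure, and causality is judged against somapacitan.** This largely disposes of the inference that reactions to a previous growth hormone enter the ADR counts. It does not cover all AEs and SAEs, because the registry's AE question (9.9) is not specific to a product. Nor does it cover neoplasm and T2DM, whose incidence rates have no stated denominator.
- **Section 9.1.2 puts the somapacitan decision before registry inclusion.** If followed, the lead is only the gap from decision to first dose. It is not an eligibility rule, however, and it fits poorly with 9.4.
- **Registrations before the study may be cut off.** Data collection starts in Q4 2024 and endpoints run for up to 10 years, so a patient registered in 2023 need not contribute time from 2023. The same sequence from 2025 onward is unaffected.
- **ADR results are descriptive and an SAP will follow.** True, and an exact week-0 definition could sit there. But the start at consent is a rule that the protocol states, not a gap left open.

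**Conclusion.** The point holds for the in-study AE, SAE, neoplasm and T2DM results of patients whose registry consent precedes their first somapacitan dose. The size is unknown. It is below 1% of in-study time if 9.1.2 is followed so that few patients have a lead and it is short (10% at three months). It is about 20% only if half the patients register two to three years early.

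Three further inferences lack support:

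- **Pre-start time is often spent on another growth hormone.** Non-naïve patients are enrolled, but no share or timing is given.
- **The neoplasm rate is necessarily diluted.** The active-malignancy exclusion (9.2.3) carries no date. If it is applied at somapacitan start, earlier time is free of active malignancy by selection and dilutes the rate. If it is applied at consent, a neoplasm before the first dose could count as incident. The direction is open.
- **The age criterion must change.** Correcting the clock does not need it.

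The reverse contradiction, for patients already treated at consent, follows from the definitions alone and needs no assumption about numbers.

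**What to change.** In 9.1 and 9.7.2.2, define baseline (week 0) and the start of both the in-study and on-treatment risk periods as the later of GloBE-Reg consent and first somapacitan dose. Keep follow-up after discontinuation in the in-study period. Treat earlier registry data as medical history. Reconcile 9.1.2 with 9.4 and the eligibility criteria, and state the date at which the malignancy exclusion is assessed.

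The somapacitan start date is already a study variable (9.3.1), so no new data are needed. The cost is a few sentences and slightly fewer in-study patient-years. For patients already on somapacitan at consent, risk time would start at consent, while treatment duration can still be counted from the recorded start date.

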9.9 Limitations of the research methods

Data collection for this study will reflect routine clinical practice rather than mandatory assessments at pre-specified time points. The study captures data in GloBE-Reg from many different regions and settings. As data collection will reflect national, regional, and local differences in routine clinical practice regarding diagnostics, laboratory analyses, and reporting of events, potential issues may arise due to the study design. These issues may result in heterogeneous reporting of specific outcomes and time points for collection. Therefore, it is important to take these differences into account during the interpretation of data.

AEs are collected into GloBE-Reg based on the answer to the below question:

"Since the last recorded clinical encounter in the GloBE-Reg registry, has the patient experienced any untoward medical occurrence (sign, symptom or disease)"

In addition, the physician is responsible for evaluating the seriousness and causality of the AEs.

The safety endpoints are therefore limited to the physician's evaluation of these questions, and due to the secondary collection of data this evaluation cannot be further investigated.

The data source for the study, GloBE-Reg, captures data from many different regions and settings. This leads to a potentially heterogeneous patient population and different local standard of care and data capture, e.g., local differences in diagnostics, laboratory analyses, and reporting of events. This could result in a risk of information bias.

There is a risk of selection bias in the study, affected by the willingness and/or ability of physicians and patients to participate in GloBE-Reg. In addition, any undiagnosed patients will not be able to participate, and the rate of underdiagnosis may vary between regions. This may lead to a selected patient population, which does not accurately reflect the underlying patient population and may result in limited data on certain subgroups.

The long-term follow-up is a strength of this non-interventional study, but also leads to a risk of loss to follow up.

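### Section 9.7.2.2 gives the on-treatment period two incompatible start dates for patients already on somapacitan at consent; under one of them, pooled on-treatment event rates are understated.

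*Protocol*

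**What the plan says.** Section 9.7.2.2 of the protocol defines two observation periods. For the first: "The in-study period starts at the time of informed consent and ends at the date of whichever comes first" of a short list of end events. For the second it states "This observation period is a part of the in-study observation period. The on-treatment period starts at the date of treatment start", followed by its own list of end events. No clause limits the start to consent or later.

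Other sections bear on who is affected and what can be observed:

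- Section 9.2.2 requires treatment with commercial somapacitan and does not restrict entry to new users. Section 9.4 describes a registry open to patients about to start a treatment and to those for whom it is being or has been considered.
- Section 9.1.2 places the decision to treat "prior to, and independently from, the decision to include the patient in the GloBE-Reg registry".
- Section 9.1: "Individual patients will be followed up from inclusion into GloBE-Reg until last routine visit within the full study duration".
- Section 9.2.6 allows no study recording before signed consent.
- Section 9.9 gives the question through which adverse events are captured, which begins "Since the last recorded clinical encounter in the GloBE-Reg registry, has the patient experienced any untoward medical occurrence (sign, symptom or disease".
- Section 9.7.2.1 expresses event rates per 100 patient-years of exposure, and Section 9.7.2.2 applies the same method to the other count endpoints.
- Section 9.3.1 lists the somapacitan start date as an extracted variable.

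**The concern.** For a child who starts somapacitan after consent, the two sentences agree. For a child already on the drug at consent, a period that begins at treatment start is not contained in a period that begins at consent. An analyst must break one sentence to obey the other.

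The choice matters because the two dates treat time at risk differently. Follow-up and event capture begin at registry entry, so treatment time before consent can add to the denominator of an on-treatment rate but nothing to its numerator. This is immortal time, and it lowers the rate. The neoplasm and T2DM incidence rates are to be set against published rates for daily GH, so a denominator that is too large makes somapacitan look safer than the data show.

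The start of week 0 does not settle the question: events are counted from baseline (week 0), but the protocol ties that point to neither consent nor first dose.

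**Working it through.** **The plan's own figures.** The protocol gives no figure for on-treatment time or for the share of patients already treated at consent, so there is none to reproduce on this point. Its sample-size table (Table 9-4, Wilson interval for a 2% proportion) recomputes to within 0.01 percentage point; for 400 patients, 1.02 to 3.90 against the stated 1.02 to 3.89. That table concerns a proportion and does not depend on the disputed start date.

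**The text, start against end.**

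1. In-study start: "The in-study period starts at the time of informed consent".
2. On-treatment start: the date of somapacitan start, with no further limit.
3. On-treatment end: the first of stopping somapacitan, the EOS visit, withdrawal of consent, or other reasons such as death. The last three are the in-study end events, written out again.

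The nesting sentence is therefore not relied on to close the period, since every in-study end event is repeated for it. Only the start lacks a matching limit, so someone programming from the explicit rules would use the recorded somapacitan start date.

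**Size under the literal start date.** Let D be the events recorded after consent, N the number of patients, T the mean on-treatment years after consent, f the share already on somapacitan at consent, and L their mean years on it before consent. No event can be recorded before consent.

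- Rate from the later of consent and first dose: D / (N × T)
- Rate from first dose: D / (N × (T + f × L))
- Ratio of the second to the first: T / (T + f × L)

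The protocol gives none of f, L or T, so all three are assumptions. For illustration take N = 400 and D = 8 (the planning proportion of 2% × 400, one event per affected patient).

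| f | L (years) | T (years) | Ratio | Understatement | Rate per 100 patient-years |
|---|---|---|---|---|---|
| 0 | any | 5 | 1.000 | 0% | 800/2000 = 0.400 |
| 0.10 | 1 | 5 | 5/5.10 = 0.980 | 2.0% | 800/2040 = 0.392 |
| 0.25 | 1 | 5 | 5/5.25 = 0.952 | 4.8% | 800/2100 = 0.381 |
| 0.50 | 1 | 5 | 5/5.50 = 0.909 | 9.1% | 800/2200 = 0.364 |
| 0.50 | 2 | 5 | 5/6.00 = 0.833 | 16.7% | 800/2400 = 0.333 |
| 0.50 | 1 | 3 | 3/3.50 = 0.857 | 14.3% | 800/1400 = 0.571, against 800/1200 = 0.667 |

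A true rate ratio of 2.0 against an external rate would appear as 2 × 0.980 = 1.96, 2 × 0.952 = 1.90 and 2 × 0.909 = 1.82 in the second to fourth rows. With the later-of rule the term f × L drops out and the ratio is 1.00 in every row.

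**The case against.** The strongest answer is that the nesting sentence already solves the problem: if on-treatment time is part of in-study time, it cannot begin before consent, and the dilution disappears. That reading is available. It does not remove the finding, because the next sentence states a different start without qualification and the repeated end events suggest that nesting was not meant to cut the period by itself. But it does mean that dilution follows from one of two readings.

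A reader might infer that every on-treatment result is diluted, perhaps by as much as a third. The documents do not support this. Counts, proportions of patients with an event, all in-study rates and rates among patients starting at or after consent are unaffected. The two periods are defined under the secondary endpoints, and the protocol does not say that they apply to the primary ADR rate. A third requires, for example, 75% already treated for two years with only three years on treatment afterwards: 3 / (3 + 0.75 × 2) = 0.667. Nothing in the protocol shows that such patients are common. Section 9.1.2 speaks of the decision to treat, not of the first dose, and the registry also takes patients about to start.

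Plausible dilution is also small beside sampling error: an exact Poisson 95% interval for 8 events runs from about 3.5 to 15.8, or −57% to +97%. That is true, but the dilution is systematic, goes in one direction and is avoidable.

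A reader might further infer that a later start date cures the absence of patients who stopped early because of a reaction. It does not. That selection comes from admitting current users, and Section 9.9 acknowledges selection bias only in general terms. Nor does this conflict show that current users should be left out of the growth endpoints: Section 9.7.2.2 already estimates change by treatment duration as well as follow-up.

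Finally, an SAP could settle the date. It could, but the protocol did not leave the matter open; it stated a rule that conflicts with the sentence beside it.

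**Conclusion.** The point holds as an internal contradiction with a one-sided consequence. For patients already on somapacitan at consent, the two sentences in Section 9.7.2.2 give different start dates. If the explicit date is applied, pooled on-treatment rates are too low by the factor T / (T + f × L).

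The size cannot be fixed from the protocol. It is about 2% to 9% for 10% to 50% already treated, one prior year and five on-treatment years after consent, and 14% for half already treated, one prior year and three years after. It is zero if nobody is treated before consent or if nesting is taken to cut the period there. These figures assume that no event before consent is counted, as the follow-up and event-capture rules imply. The direction is certain under the literal reading; the magnitude is not.

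**What to change.** In Section 9.7.2.2, start on-treatment time at risk at the later of informed consent and first somapacitan dose, and count only events with onset on or after that date. Define baseline (week 0) consistently with this rule. Keep time since first dose only as the treatment-duration variable.

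Optionally, show patients already on somapacitan at consent as a separate group. A child whose only GH before consent was somapacitan fits neither the GH-naïve group nor the group that came from another GH product. Showing them apart makes the selection of early tolerators visible but does not remove it.

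The cost is a sentence or two in the protocol and one derived date, plus one more table stratum if the option is taken. Section 9.3.1 already lists the somapacitan start date and the in-study definition already needs the consent date, so no new data are required. The sample size does not change.
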